### **12.2.1. SAE Reporting Procedure**

The Investigator or designee must report any SAE to the Sponsor or its designee immediately (within 24 hours (1 working day)) following becoming aware of the event even if the SAE does not appear to be related to IP. This timeframe also applies to becoming aware of additional new information (follow-up) on previously reported SAEs.

Do not delay reporting a suspected SAE in order to obtain additional information. Any additional information, if collected, can be reported as a follow-up to the initial report. Prompt notification of SAEs by the Investigator to the Sponsor is essential so that legal obligations and ethical responsibilities towards the safety of subjects and the safety of a product under clinical investigation are met.

If the subject was permanently withdrawn from the study due to the SAE, this information must be reported in either the initial or follow-up SAE report, and in the End of Study CRF.

For any deaths reported, available autopsy reports and relevant medical reports should be provided with the SAE report.

Specific details regarding the applicable forms, process and contacts for SAE reporting will be provided in the Study Procedures Manual.

The Investigator or designee should notify the IRB of SAEs occurring at the site and other SAE reports received from the Sponsor or its designee, in accordance with IRB procedures. The Sponsor will be responsible for notifying the relevant authorities of any SAE according to applicable regulations.

### 12.2.2. Follow-Up of Adverse Events

Following the subject's initial report of an AE, the Investigator or designee is required to proactively follow-up with the subject regarding any previous AE that hasn't resolved at subsequent visits/contacts.

Where possible, all AEs should be followed to resolution. Medically significant AEs considered related to the IP by the Investigator or the Sponsor will be followed until resolved or considered stable. Medical tests and examinations will be performed, as appropriate, to document resolution.

All SAEs will be followed until the Sponsor agrees that the event is satisfactorily resolved or that no further follow-up is required.

The Investigator will assess the outcome of each AE using the following criteria:

- **Recovered/Resolved:** The event has improved or subject recuperated.
- **Recovered/Resolved with sequelae:** The subject has recuperated but retained pathological conditions resulting from the prior disease or injury.
- **Recovering/Resolving:** The event is improving.
- **Not recovered/Not resolved:** The event has not improved, or subject has not recuperated.
- **Unknown:** The outcome of the event is not known, not observed, not recorded, or refused.
- **Fatal:** Termination of life as an outcome of the AE.

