### **12.1. Adverse Event Definitions**

An AE is any untoward medical occurrence associated with the use of a drug in humans, whether or not considered drug related. An AE can therefore be any unfavorable and unintended sign (including an abnormal laboratory finding), symptom, disease or exacerbation of a pre-existing condition temporally associated with the use of a medicinal (investigational) product.

Signs and/or symptoms of the disease under study/lack of efficacy should not be considered as AEs, as long as they are within the normal day-to-day fluctuation or expected progression of the disease. However, significant worsening (e.g., increase in severity or frequency) of the signs and/or symptoms should be recorded as an AE. Any clinically significant change from Screening, based upon the opinion of the Investigator, in physical or examination findings and/or vital signs should be recorded as an AE.

A change in the value of a safety laboratory evaluation can represent an AE if the change is clinically significant, based upon the opinion of the Investigator, or if, during treatment with the IP, a shift of a parameter is observed from a normal value to a pathological value, or a further worsening of an already pathological value. When evaluating such changes, the extent of deviation from the reference range, the duration until return to the reference range, either while continuing treatment or after the end of treatment with the IP, and the range of variation of the respective parameter within its reference range, should be taken into consideration. The Investigator should decide, based on the above criteria and the clinical condition of the subject, whether a change in a laboratory parameter represents an AE. For pathological laboratory values that were not present prior to IP administration, follow-up laboratory evaluations should be performed until the values return to within reference range or until a plausible explanation is found.

Any AE occurring after administration of IP will be considered a TEAE.

Examples of events meeting the definition of an AE **include**:

- Any abnormal laboratory test results (hematology, chemistry) or other safety assessments (e.g., physical examination, vital signs measurements), including those that worsen from Screening, and felt to be clinically significant based upon the medical and scientific judgment of the Investigator;

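### The adverse event outcome codes in Protocol Section 12.2.2 overlap, so an event that is better but still present can be coded as Recovered/Resolved

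*Protocol*

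**What the plan says.** Section 12.2.2 gives the investigator a fixed list of outcome criteria for every AE. Three of them matter here:

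- Recovered/Resolved: "The event has improved or subject recuperated".
- Recovering/Resolving: "The event is improving".
- Not recovered/Not resolved: "The event has not improved, or subject has not recuperated".

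The same section ties follow-up to resolution. The investigator must follow up proactively "regarding any previous AE that hasn't resolved at subsequent visits/contacts". As a general aim, "Where possible, all AEs should be followed to resolution". For one subset, "Medically significant AEs considered related to the IP by the Investigator or the Sponsor will be followed until resolved or considered stable".

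Two groups have end points of their own. For serious events: "All SAEs will be followed until the Sponsor agrees that the event is satisfactorily resolved or that no further follow-up is required". For pathological laboratory values that were absent before dosing, Section 12.1 says that "follow-up laboratory evaluations should be performed until the values return to within reference range or until a plausible explanation is found".

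Section 12.2 requires an outcome and, where applicable, a resolution date for each AE, and refers the outcome to Section 12.2.2. Section 13.4 plans AE descriptions by type, relationship, seriousness and severity. It does not name outcome or duration.

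**The concern.** An outcome code is useful only if each event fits exactly one category and the code for a finished event means that it is finished. The first definition fails on both counts. It accepts improvement as a sufficient condition, and it differs from Recovering/Resolving only in verb tense.

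Two things are at stake. The first is the record. Safety is the primary objective and Section 8 plans for about two sites. Two investigators could follow the protocol faithfully and still give the same course different outcomes, and the resolution date may follow the code. The second is follow-up. The word *resolved*, which ends the general duty to follow an AE, is described nowhere in the protocol except through this outcome definition.

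The statistical analysis plan cannot repair this later. The code is assigned at the site, and once an improved event has been closed the data no longer show whether it was gone.

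**Working it through.** No sample size, power or error rate bears on this point, and the protocol states no figure to reproduce. The check is to read each definition literally against four possible courses of an AE.

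| Course of the AE | Recovered/Resolved | Recovering/Resolving | Not recovered/Not resolved | Codes met |
|---|---|---|---|---|
| Gone, subject recuperated | yes (second limb) | no | no | 1 |
| Better, still present, still improving | yes (first limb) | yes | yes (second limb) | 3 |
| Better, still present, no longer changing | yes (first limb) | no | yes (second limb) | 2 |
| Present, no improvement | no | no | yes (both limbs) | 1 |

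The two extreme courses are coded cleanly. The two intermediate ones are not. In the third row the two codes that apply are opposites, and the intermediate category does not literally fit at all.

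Next, take an improved but ongoing AE that has been coded Recovered/Resolved and trace it through the follow-up rules.

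1. General duty (Sections 12 and 12.2.2): it applies to AEs that have not resolved. If the code is taken as the meaning of resolved, the duty can be read as over.
2. Medically significant related AEs (12.2.2): the rule ends at resolved or stable. It uses the same word without a separate definition, so it does not remove the ambiguity.
3. Serious AEs (12.2.2): the rule ends when the sponsor agrees. It does not depend on the investigator's code.
4. New pathological laboratory values (12.1): the rule ends at return to the reference range or a plausible explanation. It does not depend on the code.

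The exposed group is therefore mainly the non-serious, non-laboratory AEs.

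Last, trace the code into the analysis. Section 6 lists the safety evaluations as treatment-emergent AEs including serious ones, laboratory values, vital signs, ECGs and lentivirus antibodies. Neither that list nor Section 13.4 names a summary by outcome or duration. The fault reaches a recorded attribute, possibly a recorded date, and any listing that shows them.

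**The case against.** The strongest case on the other side is that a sensible investigator will not misread the list. The label says Recovered/Resolved, a separate category for events in recovery stands beside it, and Section 12.2.2 provides for tests and examinations, as appropriate, to document resolution. This makes miscoding less likely. It does not change the stated criterion, which the investigator is told to use and which says something else.

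A reader might infer more than the documents support, in four ways:

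- *That unresolved events are counted as resolved.* The text shows only that they can be coded so.
- *That follow-up stops.* The follow-up sentences do not cite the outcome codes. Besides the separate rules for serious events and laboratory values, several checks run whatever the code: the health question at each visit or contact (Section 12), the skin examination with monitoring of biopsy and injection sites at clinic visits (Skin Assessments, under 10.3.4), and the examinations, ECGs and laboratory tests scheduled through Week 12 (Table 4).
- *That duration is understated in a core safety output.* Section 12.2 records the resolution date as an item separate from the outcome, and no text sets it at the time of improvement. The code may influence the date, but duration is not a named output.
- *That one miscoded event shifts a resolved share by 1/10, or 10 percentage points.* This assumes an event type seen once in each of about 10 subjects, and a share that the protocol does not say it will report.

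These limits on the consequences stand. It is also fair to say that the CRF Completion Guidelines, listed in Section 14.7.1, are not shown and may clarify the coding. They would then be correcting the protocol's own criterion.

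**Conclusion.** Wrong as written, minor. Read literally, the Section 12.2.2 definitions let an AE that is better but still present be coded as resolved, and they let the same event meet two or three categories.

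The supported consequences are inconsistent or wrong outcome codes, possibly early resolution dates, and a possible early end to the general duty to follow unresolved AEs, mainly for non-serious, non-laboratory events. The documents give no basis for a numerical size, and no planned safety summary is shown to be affected.

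The conclusion rests on reading the listed criteria as the operative definitions, which is how Section 12.2.2 presents them, and on no other section defining *resolved*.

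**What to change.** Reword three outcome definitions in Section 12.2.2 so that they exclude one another:

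- Recovered/Resolved: the event is no longer present, or the subject has returned to the pre-event state.
- Recovering/Resolving: the event has improved but is still present.
- Not recovered/Not resolved: the event is still present with no improvement.

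All three need changing. If only the first two were reworded, an improved but ongoing event would still meet the second limb of the third. The existing category for recovery with sequelae remains for events that are over but leave a residual condition. With these definitions each of the four courses tabulated above meets exactly one code.

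Carry the same wording into the CRF guidelines. The cost is a short text edit. It changes no treatment, visit or follow-up rule, and it is cheaper before AE data accrue than querying closed events afterwards.

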### 12.2.3. Relationship of Adverse Event to Investigational Product

The relationship of an AE to IP is to be assessed by the PI using good clinical judgement and according to the following definitions:

- Not Related – no temporal association or the cause of the event has been identified, or the drug cannot be implicated based upon available information.
- Possibly Related – temporal association, but other etiologies are likely to be the cause. However, involvement of the drug cannot be excluded, based upon available information.
- Definitely Related – established temporal or other association (e.g., re-challenge) and event is not reasonably explained by the subject's known clinical state or any other factor, based on available information.

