## **7. INVESTIGATIONAL PLAN**

### **7.1. Overall Study Design**

This is an open-label, single arm Phase 1/2 study being conducted by Fibrocell to evaluate FCX-013 in subjects with moderate to severe localized scleroderma/morphea. Approximately ten subjects will be enrolled and receive FCX-013.

The study is divided into the following periods: Screening (including Manufacture), Treatment, and Long-Term Follow-Up. The Screening Period consists of entry criteria evaluations, the collection of one set of three 3-4 mm biopsies for the manufacture of FCX-013 product, and the identification of potential target sclerotic lesions. Due to the FCX-013 manufacturing process, the Screening Period is expected to have a duration of approximately 4-6 months; however, this period can be extended to accommodate subject scheduling, variations in manufacturing duration and protocol mandated delays (i.e. pauses due to staggered treatment).

After FCX-013 manufacturing is complete, Fibrocell (the Sponsor) and the Investigator will mutually agree on the planned date for injection of FCX-013.

The Treatment Period will have a 12-week duration. One administration of FCX-013 will consist of a maximum of 4 mL of FCX-013 administered in up to sixteen (16) 0.25 mL intradermal injections. On Day 1, FCX-013 will be intradermally injected, using a retro-tracing technique, into the sclerotic lesion targeted for treatment. On Day 1, following the injection of FCX-013, subjects will initiate a 14-day course of veledimex to be taken orally daily. During the Treatment Period, subjects will be evaluated at Weeks 2, 4, and 12, and have an end-of-treatment visit at Week 12.

Treatment with FCX-013 will be staggered for the first three subjects. Administering FCX-013 following each of the first three subjects requires that the previous subject complete Week 4 evaluations, and that the Investigator(s) must have received approval from the Data Safety Monitoring Board (DSMB).

Safety and clinical efficacy evaluations are conducted throughout the study. Safety will be assessed through adverse events (AEs), physical examinations, vital signs, clinical laboratory evaluations, ECGs and concomitant medications.

The Long-Term Follow-Up period is an approximately 15-year period following End of Treatment in which an examination of injection sites is conducted, and safety is monitored annually, at a minimum.

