**Table 4: Schedule of Events (Continued)**

**\*include height and weight at Baseline**

**An unscheduled visit, with necessary assessment, may occur as needed.**

Notes:

- a) For any subject who is diagnosed with or dies of a new malignancy, attempts will be made to collect a biopsy of the neoplastic tissue or pertinent autopsy tissue to perform relevant RCL testing.
- b) For any subject with a malignant growth in a region of FCX investigational gene therapy administration, attempts will be made to collect a skin biopsy of the malignant tissue for viral vector presence and potentially clonality of vector integration testing, as available.
- c) In years 1-5 only, a skin biopsy from the region of FCX investigational gene therapy administration (i.e., treated skin area) may be taken to test for relevant transgene and vector persistence *in subjects who consent to the collection of the biopsies required to perform the assay*. However, collection of biopsies will stop if transgene and vector persistence is undetected.

**\*Long-term Follow-Up for years 2-15 may be performed by contacting the subject to review/record requested information, ideally scheduled to follow annual visits and assessment (including relevant laboratory analyses) performed by the subject's health care provider.**

1. Report exposure to mutagenic agents and other medicinal products.
2. Report adverse events of special interest and emergence of new clinical conditions, including, but not limited to: new malignancy, new incidence or exacerbation of a pre-existing neurologic disorder, new incidence or exacerbation of a prior rheumatologic or other autoimmune disorder, new incidence of a hematologic disorder, unexpected illnesses and hospitalization(s).
3. Collection and analysis of a blood sample to monitor for RCL may be performed yearly for up to 15 years. If all post-treatment RCL assays are negative through one year following subject's final investigational product administration, collection of the yearly follow-up samples may be discontinued.

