### **13.4. Safety Analyses**

Subject demographics and relevant baseline data will be listed and described. Inclusion and exclusion criteria ensure that participants are suitable for the study. Premature termination will be described.

Physical examinations, vital signs, ECG data, concomitant medications, and laboratory results, including RCL analyses will be listed, and relevant changes will be described by subject and overall, as applicable.

Adverse events will be coded using the Medical Dictionary for Regulatory Activities (MedDRA) AE dictionary. Adverse events will be grouped into pre-treatment AEs and TEAEs and will be described by preferred terminology and by body system. The number of adverse event entries, as well as the number of subjects will be described, including by AE type, relationship to FCX-013 plus veledimex, seriousness, and severity of AEs.

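### The causality scale in 12.2.3 lets a delayed event be graded Not Related on timing alone and closes Possibly Related to it, which does not suit a 15-year follow-up of a lentivirally modified cell product

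*Protocol*

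**What the plan says.** Section 12.2.3 of the protocol has three grades. The relationship "is to be assessed by the PI using good clinical judgement and according to the following definitions".

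- **Not Related** has three alternatives joined by *or*. The first two are "no temporal association or the cause of the event has been identified"; the third is that what is known gives no basis for implicating the drug.
- **Possibly Related**: "temporal association, but other etiologies are likely to be the cause". The definition adds that a role for the drug cannot be ruled out.
- **Definitely Related**: begins "established temporal or other association (e.g., re-challenge") and also requires that no other factor reasonably explains the event.

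The section does not define temporal association, gives no time window and does not mention latency.

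Section 7.1 states: "The Long-Term Follow-Up period is an approximately 15-year period following End of Treatment". Footnote 2 to the Schedule of Events (Table 4) lists what is to be reported in that period. The list includes "new malignancy, new incidence or exacerbation of a pre-existing neurologic disorder", rheumatologic or autoimmune disorders and hematologic disorders. Section 13.4 describes events and subjects "including by AE type, relationship to FCX-013 plus veledimex, seriousness, and severity of AEs".

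**The concern.** Exposure is short: one FCX-013 session on Day 1 and 14 days of veledimex (9.2). The cells are modified with a lentiviral vector (5.2), and note b to Table 4 provides for vector-integration testing in a malignancy at the treated region. The protocol thus expects that harm, if it occurs, may appear years after exposure. The causality scale is written as for a conventional short-acting drug, where distance in time from dosing is evidence against causation.

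An investigator who reads temporal association as closeness in time would grade a Year 8 malignancy Not Related on the first ground alone. The wording meant for unresolved doubt sits in Possibly Related, which that event cannot enter. Safety is the primary objective. A relationship table with no related late events could then reflect the wording of the scale and not the evidence.

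**Working it through.** No figure in the plan is at issue, so the check is logical. The definitions were treated as conditions and applied to late events.

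**Step 1. Which grades can a late event receive?**

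| Late event | Not Related | Possibly Related | Definitely Related |
|---|---|---|---|
| (a) judged not temporally associated, no other link found, product role not excluded | met (first ground) | closed | closed |
| (b) judged not temporally associated, other link such as vector in tissue, no better explanation | met (first ground) | closed | met (other association) |
| (c) judged not temporally associated, other link, but another cause also plausible | met (first ground) | closed | closed |
| (d) judged temporally associated despite the delay | first ground not met | open | open |

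In (a) and (c) the only grade left is Not Related, although doubt remains. In (b) two opposite grades apply together and the text does not say which prevails. In (d) the scale works. The result depends on how the investigator reads an undefined term.

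**Step 2. How likely is evidence of another link?** Tumor tissue is to be sought but is not guaranteed (Table 4 notes a and b; section 12). Biopsies for transgene and vector persistence are optional and limited to years 1 to 5 (Table 4 note c). Yearly RCL sampling may stop if all post-treatment results are negative through one year (10.2.5, 10.3.8). Years 2 to 15 may be done by contact only (Table 4). A late event may therefore have no laboratory evidence either way, which is case (a).

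**Step 3. What uses the grade, and what does not?**

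Uses it:
- The relationship description in 13.4.
- The firm commitment in 12.2.2 to follow medically significant related events until resolved or stable. Serious events are followed regardless, so this concerns non-serious ones.
- The SAE and autoimmune suspension triggers in 7.5.1.

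Does not use it:
- Collection of adverse events up to the last contact (section 12).
- Treatment-emergent status, which has no upper time limit (12.1).
- SAE reporting to the Sponsor (12.2.1).
- Reporting of the footnote 2 conditions (Table 4).
- The cancer/vector and RCL rules, which depend on histology and assays (7.5.1).

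**Step 4. Do the suspension triggers matter late?** The synopsis puts first screening in 4Q2019 and last completion, including about 15 years of follow-up, in 2035. 2035 − 15 = 2020, so planned dosing ends at about that time. Eight years later is 2020 + 8 = 2028, when no planned administration remains to suspend. The triggers matter only while other subjects are still being dosed.

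**Step 5. Size.** With about 10 treated subjects, one event graded the other way changes the related count from 0/10 to 1/10, that is from 0% to 10%.

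**Step 6. Consistency with other sections.** The autoimmune trigger in 7.5.1 uses a grade of probably related, which 12.2.3 does not contain. Section 12.2.2 speaks of relatedness as judged by the Investigator or the Sponsor, while 12.2.3 gives the assessment to the PI.

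**The case against.** A reader might infer that late events will be classed as unrelated because they are late, so that the long-term results are empty by definition. The documents do not support that. Nothing equates late with not temporally associated, no window is set, and the PI is told to use judgement. A PI may reasonably regard a cancer at the injected site in Year 8 as compatible in time with an integrated vector. Definitely Related expressly admits a non-temporal association. All of this stands, and it limits the point to what the text permits. It does not remove the point, because the judgement must follow the definitions and these make timing sufficient for Not Related.

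It can also be said that the third ground for Not Related, no basis in the available information for implicating the drug, would often give the same grade. That is fair. But it turns on evidence, which is a proper basis for the grade, whereas the first ground lets calendar time decide.

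The strongest objection concerns consequences. Late events are still collected, stay treatment-emergent, and are reported if serious whatever their grade. The cancer and RCL rules bypass the scale. In a descriptive study of about 10 subjects, a late malignancy would be visible in the listings. This stands in full: the harm is to how events are attributed, not to whether they are found.

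A reader might also take the large share of observation time that falls in long-term follow-up as a measure of effect. It shows only how long the rule applies and says nothing about how often an event would be misgraded.

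**Conclusion.** The point holds as a defect in a stated rule. Section 12.2.3 allows a delayed event to be graded Not Related on timing alone. It closes Possibly Related to any event judged not temporally associated, and it lets a late event with another link meet two opposite grades. The wording can bias the relationship description in 13.4 towards Not Related and weaken the follow-up commitment for non-serious events in 12.2.2. Its effect on the 7.5.1 suspension triggers is confined to the period when dosing is still under way.

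How often it would occur cannot be estimated from the protocol. The size given, 0/10 against 1/10, assumes about 10 treated subjects, one late event in one of them, and an investigator who reads temporal association as closeness in time. The change is worth making because the study's primary objective is safety and the correction is small.

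**What to change.** In 12.2.3:

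1. State that time since administration alone is not a ground for Not Related for delayed events in Long-Term Follow-Up, namely new malignancy and neurologic, rheumatologic or autoimmune, and hematologic disorders.
2. Change the condition for Possibly Related to a temporal or other plausible association, including delayed effects of the integrated vector. Word the first ground of Not Related to match (neither kind of association present), so that the categories neither overlap nor leave a gap.
3. Reconcile the grades with 7.5.1, which uses probably related, and the assessor with 12.2.2, which names the Investigator or the Sponsor.

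An automatic grade of at least Possibly Related for every footnote 2 condition is not advised. That list also covers unexpected illnesses and hospitalizations, so such a default would fill the table with events that have no plausible link.

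The cost is a few sentences in the protocol and matching CRF guidance. The downside is that a few more late events may be listed as possibly related.

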#### **7.5. Dose Adjustment Criteria**

##### **7.5.1. Safety Criteria for Adjustment or Stopping Doses**

An objective of this study is to generate a safety profile of FCX-013 plus veledimex in subjects with moderate to severe localized scleroderma/morphea. To minimize risk, cumulative safety data will be reviewed by the Medical Monitor. Events that will result in immediate enrollment discontinuation and treatment discontinuation for all subjects are a positive RCL assay and histologically confirmed cancer in combination with the presence of viral vector in the tumor. In addition, the Medical Monitor may interrupt study dosing and/or study entry at any time if medically indicated.

Occurrence of any of these observations will trigger a temporary suspension of FCX-013 plus veledimex administration pending a safety investigation:

- A treatment emergent SAE or suspected SAE related to FCX- 013, the FCX-013 administration procedure, veledimex administration or any other protocol procedure.
- A positive RCL quantitative polymerase chain reaction (qPCR) assay result. A positive RCL qPCR assay will result in suspension of FCX-013 administration. The result will be confirmed by conducting a biological-based assay. If both assays are positive, FCX-013 administration will be discontinued and no further enrollment into the study will be allowed.
- An autoimmune response determined by the Investigator to be possibly, probably or definitely related to treatment.
- Any systemic infection designated as suspected to be related to FCX-013.
- A treatment emergent uncontrolled bacterial, viral, or fungal infection in a lesion that was administered by investigational product (IP) where product sterility testing results reported post injection were positive for contamination.
- Any subject diagnosed with a histologically proven skin cancer (including sarcomas) will be biopsied and assayed for viral vector by qPCR. A positive result for viral vector will cause product administration to be suspended.
- Abnormal laboratory value(s) or clinically significant change from screening/baseline that pose a risk to safe participation.
- Abnormal test procedure result(s) or clinically significant change from screening/baseline that pose a risk to safe participation (e.g., Grade 2 or above Common Terminology Criteria for Adverse Events/CTCAE criteria (v.4.03) for ECG test).

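### The three relatedness definitions in Protocol 12.2.3 leave no middle grade for an event that follows dosing with no cause found, so the same facts can be graded at either extreme

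*Protocol*

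**What the plan says.** Protocol 12.2.3 gives the task to the principal investigator: "The relationship of an AE to IP is to be assessed by the PI using good clinical judgement". Three definitions go with that judgement.

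- *Not Related* has three alternatives, any one of which is enough. The first is that the timing does not fit, the second is that a cause has been found, and the third reads "or the drug cannot be implicated based upon available information". The third is the one that matters here.
- *Possibly Related* applies where there is "temporal association, but other etiologies are likely to be the cause". A further sentence adds that the drug's involvement cannot be ruled out.
- *Definitely Related* calls for "established temporal or other association (e.g., re-challenge) and event is not reasonably explained". The explanations to be set aside include the clinical condition of the subject, judged on what is known at the time.

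The grade is used in several places. Section 13.4 describes adverse events by relationship to FCX-013 plus veledimex, and safety is the primary objective in section 6. Section 12.2.2 extends follow-up for medically significant events considered related. Section 7.5.1 lists, among the events that suspend dosing pending a safety investigation, "A treatment emergent SAE or suspected SAE related to" the product, its administration, veledimex or any other protocol procedure. A separate trigger in 7.5.1, for autoimmune responses, names three levels of relationship: possibly, probably and definitely.

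Section 12.2.1 requires SAE reports within 24 hours and instructs: "Do not delay reporting a suspected SAE in order to obtain additional information".

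**The concern.** A relatedness scale should give each event one grade, and two investigators with the same facts should reach the same one. This scale fails for an ordinary case: something happens soon after injection or during the veledimex course, and nobody yet knows why. Because SAEs must be reported before work-up is complete, a first SAE report will often be in that state.

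Two things are at stake. The tabulation by relationship in 13.4 is a reported part of the primary safety evaluation, and in a study of about 10 subjects each grade carries visible weight. The SAE suspension trigger in 7.5.1 also turns on relatedness, so an unclear grade leaves it unclear whether the trigger is met. The levels named in 7.5.1 do not match those in 12.2.3, so the two sections cannot be applied together as written.

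**Working it through.** The protocol gives no figure to reproduce here. The check applies each definition in 12.2.3 to one set of facts: the event follows dosing, no cause has been identified, no other cause is considered likely, and little information is available yet.

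| Grade | Condition | Met on these facts? |
|---|---|---|
| *Not Related* (any one suffices) | No temporal association | No |
| | Cause identified | No |
| | Drug cannot be implicated on the information available | Depends on the reader |
| *Possibly Related* (all needed) | Temporal association | Yes |
| | Other causes likely | No |
| | Drug's involvement cannot be excluded | Yes |
| *Definitely Related* (both needed) | Established temporal or other association | Depends on the reader |
| | Not reasonably explained otherwise on the information available | Yes |

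**Step 1: the middle is closed.** *Possibly Related* fails on its second condition. The sentence that the drug cannot be excluded is added to that condition and does not replace it. This is the firmest part of the check and needs no contestable reading.

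**Step 2: the ends are both open to a reader.** The outcome turns on what timing alone is worth.

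- If timing implicates the drug and counts as an established association, the third limb of *Not Related* fails and *Definitely Related* is met.
- If timing alone does not implicate the drug, the third limb of *Not Related* is met.
- If timing is enough to implicate the drug but too little to be an established association, no grade fits.

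The first two readings put the same event at opposite ends. The third shows that the scale is not exhaustive.

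**Step 3: compare the levels.** Section 12.2.3 defines not, possibly and definitely. The autoimmune trigger in 7.5.1 uses possibly, probably and definitely. The *probably* level has no definition, so an investigator using the 12.2.3 scale cannot assign it.

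**Step 4: size.** Sections 7.1 and 7.2 plan for about 10 subjects. If one subject's only event of a given type is graded at one end rather than the other, the related-event incidence is 0/10 = 0% or 1/10 = 10%, a difference of 10 percentage points. For *k* such subjects the difference is *k* × 10 points. The protocol gives no basis for estimating *k*.

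**The case against.** Two stronger conclusions are tempting, and the protocol supports neither.

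**A reader might infer that missing information is counted as no relationship, so that related events are undercounted.** The text does not say so. *Not Related* speaks of a drug that cannot be implicated, which permits that grade before work-up but does not compel it. An investigator who holds that close timing and no other explanation do implicate the drug is within the wording, and must then consider *Definitely Related*. Misgrading can go up as well as down, so no direction of bias is shown. Nor does 13.4 say that it tabulates the provisional grade from the first report. Sections 12.2.1 and 12.2.2 provide for follow-up, which may lead to a revised grade.

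**A reader might infer that an unexplained SAE graded unrelated would leave dosing running.** The SAE trigger in 7.5.1 does not cite 12.2.3 or make the investigator's grade decisive, whereas the autoimmune trigger in the same list does name the investigator. The SAE trigger also covers procedures, which 12.2.3 does not grade, and 12.2.2 recognises a relatedness judgement by the sponsor. Every SAE reaches the sponsor within 24 hours whatever its grade. The Medical Monitor may interrupt dosing at any time, the DSMB reviews cumulative safety data (7.7), its approval gates dosing after each of the first three subjects (7.1), and the laboratory and test-result triggers need no relatedness.

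These points limit the consequence, and they stand. They do not repair the definitions. Several safeguards are discretionary, and the stagger covers only the first subjects. The word suspected in the SAE trigger most naturally qualifies the SAE and not its relationship, so it does not settle the matter. The reference to clinical judgement does not help either, because judgement is to be used together with the definitions. Nor can this be left to an analysis plan, since the definitions govern grading at the site.

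**Conclusion.** The definitions in 12.2.3 are neither mutually exclusive nor exhaustive. An event that follows dosing with no cause found and no likely alternative cannot be *Possibly Related* and can be placed at either end by investigators who both follow the text. The *probably* level in 7.5.1 has no counterpart on the scale. As a result, the tabulation by relationship in 13.4 is unreliable for such events, in either direction, and it is unclear whether they meet the relatedness-based SAE trigger.

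The 10 percentage points per regraded subject assume 10 dosed subjects and one subject changing category. That figure shows how coarse the table is; it is not an estimate of expected error. The conclusion on the middle grade rests on reading the conditions of *Possibly Related* as cumulative, which is how they are written. This is worth correcting, but existing oversight limits the safety consequence.

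**What to change.** Reword 12.2.3 so that each event falls in exactly one category:

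- Let *Possibly Related*, or an added intermediate level, cover a temporally associated event of unknown cause where involvement of the product cannot be excluded.
- Clarify the third limb of *Not Related* so that incomplete information alone does not satisfy it.
- Reconcile the levels named in 7.5.1 with the scale, either by defining *probably* in 12.2.3 or by removing it from 7.5.1, and state whose relatedness assessment the SAE trigger uses. Which grades trigger suspension is for the sponsor to decide.

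The cost is a change to the definitions, a matching edit in 7.5.1, and an update to the CRF completion guidelines. The downside is some more *Possibly Related* grades and so a slightly less favourable related-event count.
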